#### **5.4.1. Liver Chemistry Stopping Criteria**

**Liver chemistry stopping and increased monitoring criteria** have been designed to assure subject safety and evaluate liver event etiology (in alignment with the FDA premarketing clinical liver safety guidance).

## Liver Chemistry Stopping and Increased Monitoring Algorithm

### Liver Chemistry Increased Monitoring Algorithm with Continued Therapy for ALT $\geq 3$ xULN but < 8xULN

Liver Safety Required Actions and Follow up Assessments Section can be found in Section 12.5. Appendix 5

#### 5.4.1.1. Study Treatment Restart or Rechallenge

Study treatment restart or rechallenge after liver chemistry stopping criteria are met by any subject participating in this study is not allowed.

#### 5.5. Subject and Study Completion

A completed subject is one who has completed all periods of the study including the follow-up visit. The study will be completed with the last subject's last study visit.

### 6. STUDY TREATMENTS

#### 6.1. Investigational Product and Other Study Treatment

The term 'study treatment' is used throughout the protocol to describe any products received by the subject as per the protocol design. Accordingly, 'study treatment' sometimes refers to each product and sometimes refers to multiple products.

#### GSK1278863 (study drug)

The study drug GSK1278863 will be supplied as fast-release film coated tablets for oral administration containing 1 mg, 2 mg, 4 mg, or 6 mg of GSK1278863 (Table 2). There are two sizes of GSK1278863 tablets.

**Table 2 Description of GSK1278863 Tablets**

GSK1278863 tablets of specific content	Description
1 mg tablets, 2 mg tablets, 4 mg tablets	7.0 mm round, standard biconvex, white film coated tablets containing 1 mg, 2 mg, or 4 mg of GSK1278863 as active ingredient
6 mg tablets	9.0 mm round, standard biconvex, white film coated tablets containing 6 mg of GSK1278863 as active ingredient

GSK1278863 tablets of specific content are packed in high density polyethylene (HDPE) bottles, with 35 tablets per bottle. Subjects are to take one to four tablets (Table 3) with water once daily according to the dose level indicated at each study visit. Subjects can take GSK1278863 tablets without regard to food or peritoneal dialysis. The administration schedule (starting dose and dose adjustment) described in Section 6.4.1. should be followed.

**Table 3 Dose Levels of GSK1278863 and Number of Tablets Taken**

Dose level of GSK1278863 (once daily)	1 mg	2 mg	4 mg	6 mg	8 mg	12 mg	18 mg	24 mg
Number of GSK1278863 tablets taken	1 mg tablet ×1	2 mg tablet ×1	4 mg tablet ×1	6 mg tablet ×1	4 mg tablet ×2	6 mg tablet ×2	6 mg tablet ×3	6 mg tablet ×4

Subjects should be instructed to bring GSK1278863 tablets with bottles at each study visit, and all unused GSK1278863 tablets will be collected from subjects at each study visit.

### **Epoetin beta pegol (control)**

The control epoetin beta pegol (brand name: Mircera® Pre-filled Syringe) will be supplied by GSK. This product is an injectable formulation containing 25 µg, 50 µg, 75 µg, 100 µg, 150 µg, 200 µg, or 250 µg of epoetin beta pegol per syringe (0.3 mL) and is supplied as a glass syringe prefilled with epoetin beta pegol solution (clear colorless to pale yellow). Subjects are to receive epoetin beta pegol subcutaneously once every 2 or 4 weeks at the site ([Table 4](#)). The administration schedule (starting dose and dose adjustment) described in Section [6.4.2](#). should be followed.

**Table 4 Dose Levels of Epoetin Beta Pegol and Number of Subcutaneous Doses**

Dose level of epoetin beta pegol (once every 2 or 4 weeks)	25 µg	50 µg	75 µg	100 µg	150 µg	200 µg	250 µg
Number of subcutaneous doses of epoetin beta pegol	25 µg injection ×1	50 µg injection ×1	75 µg injection ×1	100 µg injection ×1	150 µg injection ×1	200 µg injection ×1	250 µg injection ×1

### **6.2. Medical Devices**

The Epoetin beta pegol (Brand name :MIRCERA® Injection Syringe) marketed with the device (kit formulation which was filled liquid medication in glass syringe ) provided for use in this study. Instructions for medical device are described in the Prescribing Infomration of MIRCERA® Injection Syringe.

The medical device incidents, including those resulting from malfunctions of the device, must be detected, documented, and reported by the investigator throughout the study – see Section 7.4.4.

### **6.3. Treatment Assignment**

The randomization schedule will be generated by GlaxoSmithKline (GSK) using the randomization system (Randall).

In Cohort 1 (ND subjects), subjects will be stratified by the current ESA therapy (ESA non-user or ESA user) and the Hgb level on Day 1 and randomized in a 1:1 ratio to one of the two treatment groups according to the randomization schedule. Randomization should precede the study treatment.

- GSK1278863 group
- Epoetin beta pegol group

In Cohort 2 (PD subjects), all eligible subjects will start treatment with GSK1278863 on Day 1.

Subjects will be assigned a randomization number by the Interactive Web Recognition System (IWRS). Once a randomization number has been assigned, it must not be re-assigned. Further details are provided in the Study Reference Manual (SRM).

## 6.4. Administration Schedule (Starting Dose, Dose Adjustment, and Dosing Frequency)

### 6.4.1. GSK1278863 (ND and PD Subjects)

#### 6.4.1.1. Starting Dose

For ND (Cohort 1) and PD subjects (Cohort 2) randomized to the GSK1278863 group, both ESA non-users and users will start oral treatment with GSK1278863 at the starting dose of 4 mg once daily (Day 1) and remain on the same regimen until the day of Week 4.

ESA users should skip ESA on Day 1 when treatment with GSK1278863 is started.

#### 6.4.1.2. Maintenance Dose

From Weeks 4 to 52, interruption of treatment or dose adjustments will be made within the maintenance dose range of 1-24 mg ([Table 5](#)) according to the dose adjustment algorithm ([Table 6](#)) to achieve and/or maintain Hgb within the target range (11.0-13.0 g/dL) based on the HemoCue Hgb value measured every 4 weeks. Dose changes will be made every 4 weeks. If any of the one-step dose reduction criteria is met during treatment at the minimum maintenance dose (1 mg), treatment should be interrupted; once the one-step dose increase criteria are met, treatment at 1 mg will be resumed. If the one-step dose increase criterion is met during treatment at the maximum maintenance dose (24 mg), treatment at 24 mg should be continued.

**Table 5 Maintenance Dose of GSK1278863**

Dose step	1	2	3	4	5	6	7	8
Dose level of GSK1278863 (once daily)	1 mg	2 mg	4 mg	6 mg	8 mg	12 mg	18 mg	24 mg
Number of GSK1278863 tablets taken	1 mg tablet ×1	2 mg tablet ×1	4 mg tablet ×1	6 mg tablet ×1	4 mg tablet ×2	6 mg tablet ×2	6 mg tablet ×3	6 mg tablet ×4

**Table 6 Dose Adjustment Algorithm (GSK1278863)**

Hgb (g/dL)	Hgb increase over 4 weeks (g/dL)	Treatment
>13.0	NA	Interrupt treatment until Hgb decreases to less than 12.5 g/dL Resume treatment at the one lower dose level (If interrupted at 1 mg: resume treatment at 1 mg once the one-step dose increase criteria are met)
12.5-13.0	NA	One-step dose reduction
11.5-<12.5	>2.0	One-step dose reduction
	≤2.0	Continue treatment at the current dose level
7.5-<11.5	>2.0	One-step dose reduction
	0.5-2.0	Continue treatment at the current dose level
	<0.5	One-step dose increase
<7.5	NA	Discontinue treatment permanently * and initiate another appropriate treatment

\*: If an initial Hgb value is less than 7.5 g/dL, measurement will be repeated at the same study visit (using the same sample) to calculate the average. If the average meets the Hgb stopping criteria, study treatment will be permanently discontinued.

#### 6.4.2. Epoetin Beta Pegol (ND Subjects Only)

For ND subjects (Cohort 1) randomized to the epoetin beta pegol group, ESA non-users and users will receive epoetin beta pegol subcutaneously according to the treatment regimens described below.

##### 6.4.2.1. Starting Dose for ESA Non-users

ESA non-users will start subcutaneous treatment with epoetin beta pegol at a dose of 25 µg once every 2 weeks (Day 1). Dose adjustments will be made within the initial dose range of 25-150 µg (Table 7) according to the dose adjustment criteria (Table 8) to increase Hgb to 11.0 g/dL (lower limit of the target) or more based on the HemoCue Hgb value measured every 4 weeks. Dose changes will be made every 4 weeks. If any of the dose reduction criteria shown in Table 8 is met during treatment with epoetin beta pegol at 25 µg, treatment should be interrupted; once the dose reduction criteria are not met any longer, treatment will be resumed at a dose of 25 µg.

**Table 7 Initial Dose of Epoetin Beta Pegol (ESA Non-users)**

Dose step	1	2	3	4	5
Dose level of epoetin beta pegol (once every 2 weeks)	25 µg	50 µg	75 µg	100 µg	150 µg

**Table 8 Initial Dose Adjustment Criteria for Epoetin Beta Pego (ESA Non-users)**

Hgb	Treatment
Hgb increase <1.0 g/dL over past 4 weeks, OR Hgb <10.0 g/dL and Hgb increase ≤2.0 g/dL over past 4 weeks	One-step dose increase
Hgb increase >2.0 g/dL over past 4 weeks	One-step dose reduction
Otherwise	Continue treatment at the current dose level

Once Hgb increases to 11.0 g/dL or more, dose adjustments will be made according to the prespecified dose adjustment algorithm (Table 12). The dosing interval should be changed from once every 2 weeks to once every 4 weeks with dose conversion for dosing interval change (Table 9) after it is confirmed that all of the following criteria are met:

- Hgb in the target range (11.0-13.0 g/dL)
- Hgb change  $\leq 2.0$  g/dL over past 4 weeks
- Equivalent dose will be given twice (at least 4 weeks)

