#### **5.4. Withdrawal/Dropout Criteria**

If subjects meet one of the following criteria, study treatment should be permanently discontinued and subjects will be withdrawn from the study. The withdrawal reason should be recorded.

- Hgb <7.5 g/dL  
Note: HemoCue Hgb values will be employed. If an initial Hgb value meets the Hgb stopping criteria, measurement will be repeated at the same study visit (using the same sample) to calculate the average. If the average meets the Hgb stopping criteria, study treatment will be discontinued.
- Subject needs for maintenance dialysis or changes dialysis modality (PD subjects only) during the study period.
- Kidney transplant
- Subject becomes pregnant or intends to become pregnant during the study.
- Diagnosis of new or recurrent cancer
- Liver chemistry abnormalities exceeding the threshold criteria (see Section [5.4.1.](#))
- Need for chronic (more than 14 days) use of prohibited medication
- When the investigator (or subinvestigator) considers necessary to withdraw the subject from the study for other reasons

Subjects who meet any of the withdrawal criteria or are withdrawn for other reasons during the treatment phase should be assessed at withdrawal visit after study treatment is discontinued, and will then enter the follow-up phase.

Should a subject fail to attend a required study visit, the investigator (or subinvestigator) should take the following measures:

[figure not shown]
- The investigator (or subinvestigator) or designee should attempt to contact the subject and reschedule the missed visit as soon as possible.
- The investigator (or subinvestigator) should counsel the subject on the importance of maintaining the assigned visit schedule and determine whether the subject is willing to continue his/her participation in the study and/or whether the subject should remain in the study.
- The investigator (or subinvestigator) or designee should make every effort to regain contact with a subject who is deemed “Lost to Follow-up”. All efforts to contact the subject should be documented in the subject’s clinical charts.
- Should the subject continue to be unreachable, then and only then will he/she be considered “Lost to Follow-up.”

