**Table 12 Dose Adjustment Algorithm (Epoetin Beta Pegol)**

Hgb (g/dL)	Hgb increase over 4 weeks (g/dL)	Treatment
>13.0	NA	Interrupt treatment until Hgb decreases to less than 12.5 g/dL Resume treatment at the one lower dose level (resume treatment at 25 µg if interrupted at 25 µg)
12.5-13.0	NA	One-step dose reduction
11.5-<12.5	>2.0	One-step dose reduction
	≤2.0	Continue treatment at the current dose level
7.5-<11.5	>2.0	One-step dose reduction
	1.0-2.0	Continue treatment at the current dose level
	<1.0	One-step dose increase
<7.5	NA	Discontinue treatment permanently * and initiate another appropriate treatment

\*: If an initial Hgb value is less than 7.5 g/dL, measurement will be repeated at the same study visit (using the same sample) to calculate the average. If the average meets the Hgb stopping criteria, study treatment will be permanently discontinued.

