## 7.3. Efficacy

Efficacy will be assessed according to the Time and Event Table ([Table 13](#)).

Hgb concentrations measured by the central laboratory will be mainly used for efficacy assessment (see Section 7.4.7.).

GSK will supply a point-of-care Hgb analyzer (HemoCue) to each site for rapid and convenient measurement of Hgb and to ensure consistency of Hgb measurements across all sites participating in the study. Assessment for Hgb concentrations via HemoCue will be used for eligibility (Section 5.1.), withdrawal (Section 5.4.), and dose adjustment criteria (Section 6.4.).

In addition, assessments of iron metabolism parameters and measures of CKD progression (e.g., eGFR) used for efficacy assessment are outlined with specific procedures in Section 7.4.7..

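### Table 8, the initial dosing table for control-arm ESA non-users, has no lower Hgb bound, so read literally it raises the dose at a confirmed Hgb below 7.5 g/dL, where Section 5.4 requires permanent discontinuation

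*Protocol*

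**What the plan says.** Section numbers are those of Protocol Amendment 01.

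- **Section 6.4.2.1 and Table 8.** ESA non-users randomized to epoetin beta pegol start on a two-weekly schedule and are adjusted every 4 weeks by Table 8, using HemoCue Hgb. A one-step increase applies if either of two conditions holds: "Hgb increase <1.0 g/dL over past 4 weeks", "OR Hgb <10.0 g/dL and Hgb increase ≤2.0 g/dL over past 4 weeks". A rise above 2.0 g/dL leads to a reduction, and anything else continues the current dose. There is no row for Hgb below 7.5 g/dL, no footnote and no reference to Section 5.4.
- **Handover, below Table 8.** "Once Hgb increases to 11.0 g/dL or more, dose adjustments will be made according to the prespecified dose adjustment algorithm (Table 12"). Until then Table 12 does not govern these subjects.
- **Section 5.4.** "If subjects meet one of the following criteria, study treatment should be permanently discontinued and subjects will be withdrawn from the study". Hgb below 7.5 g/dL is the first criterion listed, with no limit by arm, cohort or dosing phase. A first reading that meets it is repeated on the same sample at the same visit: "If the average meets the Hgb stopping criteria, study treatment will be discontinued".
- **Tables 6 and 12** (GSK1278863, and epoetin beta pegol maintenance). Each has a row for Hgb below 7.5 g/dL: "Discontinue treatment permanently * and initiate another appropriate treatment". In each, a footnote restates the repeat measurement.
- **Sections 4.2 and 7.3.** HemoCue Hgb serves both withdrawal and dose adjustment.

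**The concern.** Three tables tell a site what to do with the HemoCue value in front of it. Two contain the stop at 7.5 g/dL, with the repeat reading. The third, used only in the control arm and only before Hgb first reaches 11.0 g/dL, contains neither, and its increase row is open at the bottom. A site working from Table 8 alone would raise the dose on a value at which a site working from Section 5.4 stops treatment and withdraws the subject.

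The protocol foresees such values: the number of subjects with Hgb below 7.5 g/dL is a listed secondary endpoint in Section 3. ESA non-users may enter from 8.0 g/dL, so for those at the bottom of the entry range the gap to the threshold is 8.0 - 7.5 = 0.5 g/dL. Section 7 allows no waivers except for immediate safety concerns, so the text should not leave a site to choose between two instructions. Section 4.4 also relies on prespecified Hgb-based dosing in both groups to justify the open-label design, which is a reason to keep the dosing tables consistent with the withdrawal rule.

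**Working it through.** No sample size, power or alpha figure bears on this point. The check is whether Table 8 and Section 5.4 can apply to the same subject at the same visit, and what each then requires.

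**Inputs.** Current Hgb is h, Hgb 4 weeks earlier is p, and the change is d = h - p.
- Table 8 increases the dose if d < 1.0, or if h < 10.0 and d ≤ 2.0.
- Table 12 discontinues if h < 7.5.
- Section 5.4 discontinues and withdraws if the average of the two readings is < 7.5.
- Entry Hgb for ESA non-users is 8.0 to < 11.0 g/dL (Section 5.1).

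**General argument.** A subject still on treatment had p ≥ 7.5 at the previous visit, or p ≥ 8.0 at baseline. If h < 7.5 now, then d < 0. Hence d < 1.0, and also h < 10.0 with d ≤ 2.0, so both increase conditions hold. The reduction row needs d > 2.0 and cannot apply, and nothing is left for the row that continues the current dose.

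**Grid check, in steps of 0.1 g/dL.** The grid is an assumption chosen to span the case.

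| Situation | Combinations | Table 8 says increase | Section 5.4 threshold met |
|---|---|---|---|
| h from 5.0 to 7.4, p from 7.5 to 10.9 | 25 × 35 = 875 | 875 | 875 |
| Week 4: h from 5.0 to 7.4, baseline from 8.0 to 10.9 | 25 × 30 = 750 | 750 | 750 |

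Table 12 applied to the same 875 pairs gives discontinuation in all 875. The counts confirm the algebra and say nothing about how often such values occur.

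**The repeat reading.** The conflict exists only at the confirmed value. With a first reading of 7.2 and a repeat of 7.9, the average is (7.2 + 7.9)/2 = 7.55; Section 5.4 is not met and there is no conflict. With a repeat of 7.4, the average is (7.2 + 7.4)/2 = 7.30. Section 5.4 then requires a stop, while Table 8 still reads as an increase.

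**Subjects dosed under Table 8.** Cohort 1 has 270 subjects, with at least 50 ESA users and at least 50 non-users, so non-users number between 50 and 270 - 50 = 220. Randomization is 1:1 and stratified by ESA use. Assuming an even split, the control arm holds about 50/2 = 25 to 220/2 = 110 of them, out of 135. This is the pool that starts under Table 8, not a count of events.

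**Power.** The stated figures depend only on 100 subjects per group, SD 1.5 and margin -1.0. The standard error is 1.5 × √(2/100) = 0.212. The t-test power is 0.9968 (stated 99.7%), and the smallest observed difference that still shows non-inferiority is -0.5817 (stated -0.582). Neither depends on Table 8.

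**The case against.** The strongest reply is that Section 5.4 already settles the matter. It is mandatory and study-wide, and a dose-step table addresses subjects who remain on treatment. None of Tables 6, 8 and 12 has a row for the pregnancy, cancer, transplant or liver stops, and nobody would read them as ordering continued dosing in those cases. The rows below 7.5 g/dL in Tables 6 and 12 restate Section 5.4, so leaving the restatement out of Table 8 does not cancel the rule. Table 8 also never names 7.5 g/dL; the overlap comes from an open lower end.

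Much of this stands, and Section 5.4 is the more natural reading. What it does not remove is the asymmetry. The other stops are absent from all three tables, whereas the Hgb stop is written into two and missing from one. Hgb is also the quantity that Table 8 itself acts on, so a literal reading yields an answer and not silence. Nothing in Section 6.4.2.1 or Table 8 defers to Section 5.4.

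Several stronger readings are tempting and not supported:

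- *The arms would be treated differently, biasing Weeks 40 to 52.* Section 5.4 applies equally to both arms. A difference arises only if sites disregard it, and Table 8 says nothing about staying in the study.
- *Between 25 and 110 subjects are affected.* That is the pool; the protocol gives no rate of falling below 7.5 g/dL.
- *A single reading of 7.2 triggers the stop.* Section 5.4 acts on the average.
- *The interactive web system (IWRS) would assign the wrong dose.* The protocol describes registration and assignment of randomization numbers through it. It does not say that the system applies the dosing algorithm.

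**Conclusion.** The inconsistency is real and confined to one table. For a control-arm ESA non-user not yet at 11.0 g/dL, a confirmed HemoCue Hgb below 7.5 g/dL meets the increase row of Table 8 and the withdrawal criterion of Section 5.4 together, in every case where the previous value was at or above 7.5. This rests on reading Table 8 literally and on the confirmed, averaged value. Most sites would probably follow Section 5.4, so what is at stake is inconsistent handling in part of one arm, on a safety-relevant value. The documents do not establish a difference between arms or bias in the primary comparison. The frequency is unknown and the sample size and power are unaffected. The severity is minor to moderate: worth correcting because the instructions are opposite and the correction is nearly free, but not a condition for the trial to proceed.

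**What to change.** Reconcile Table 8 and Section 6.4.2.1 with Section 5.4 and with the rows below 7.5 g/dL in Tables 6 and 12. A row, a footnote or a cross-reference would do, provided that one instruction, including the repeat-measurement step, applies at a confirmed Hgb below 7.5 g/dL. Which passage governs is a clinical decision for the sponsor and is not judged here. If, and only if, the IWRS assigns doses, check that its logic follows the reconciled text.

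The cost is one line in the next amendment and a short note to sites. Sample size, visits and the planned analyses do not change.

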**Table 9 Dose Conversion of Epoetin Beta Pegol for Dosing Interval Change (ESA Non-users)**

Initial dose of epoetin beta pegol (given once every 2 weeks)		Dose conversion of epoetin beta pegol (given once every 4 weeks)
25 µg	→	50 µg
50 µg	→	100 µg
75 µg	→	150 µg
100 µg	→	200 µg
150 µg	→	250 µg

#### 6.4.2.2. Dose Conversion for ESA Users

For ESA users, prior ESA will be replaced with epoetin beta pegol at the equivalent dose once every 4 weeks (Day 1).

**Table 10 Replacement with Epoetin Beta Pegol-Initial Dose (ESA Users)**

Prior ESA		Epoetin beta pegol
Epoetin	<4500 IU per week	100 µg once every 4 weeks
	≥4500 IU per week	150 µg once every 4 weeks
Darbepoetin alfa	30 µg once every 4 weeks *	25 µg once every 4 weeks
	60 µg once every 4 weeks *	50 µg once every 4 weeks
	90 µg once every 4 weeks *	75 µg once every 4 weeks
	120 µg once every 4 weeks *	100 µg once every 4 weeks
	180 µg once every 4 weeks *	150 µg once every 4 weeks
Epoetin beta pegol	25, 50, 75, 100, 150, 200, 250 µg once every 4 weeks *	25, 50, 75, 100, 150, 200, 250 µg once every 4 weeks

\*: Allowance of  $\pm 1$  week

Maintenance treatment will be started at Week 4 as described in Section 6.4.2.3.

#### 6.4.2.3. Maintenance Dose (ESA Non-users and Users)

Epoetin beta pegol will be administered once every 4 weeks from dosing interval change (once every 4 weeks) with Hgb  $\geq 11.0$  g/dL to Week 52 in ESA non-users and from Weeks 4 to 52 in ESA users. Interruption of treatment or dose adjustments will be made within the maintenance dose range of 25-250 µg (Table 11) according to the dose adjustment algorithm (Table 12) to achieve and/or maintain Hgb within the target range (11.0-13.0 g/dL) based on the HemoCue Hgb value measured every 4 weeks. If any of the one-step dose reduction criteria is met during treatment at the minimum maintenance dose (25 µg), treatment should be interrupted; once the one-step dose reduction criteria

are not met any longer, treatment at 25 µg will be resumed. If the one-step dose increase criterion is met during treatment at the maximum maintenance dose (250 µg), treatment at 250 µg should be continued.

